7.4.3.13 Patients’ Global Impression of Change (PGIC)

Patients’ Global Impression of Change will be summarized descriptively by visit, treatment arm and type of ESA treatment.

7.4.3.14 Changes from BL to each study visit (when measured) in Serum hepcidin, Serum ferritin, TSAT and HbA1c level.

Changes from baseline to each study visit will be calculated for these parameters:

- Serum hepcidin
- Serum ferritin
- TSAT
- Serum Iron
- TIBC
- HbA1c level (Subjects with diabetes, Subjects without diabetes, and overall)

Descriptive statistics and frequency tabulations will be presented for these parameters and for the change from baseline by visit, treatment arm and type of ESA treatment. Mean values will also be plotted versus visit by treatment arm.

7.4.4 Analysis of Exploratory Variables: hs-CRP (High Sensitivity C-Reactive Protein) and Post-dialysis BP.

For each visit, descriptive statistics with the absolute values and change from baseline for hs-CRP will be displayed by treatment arm and type of ESA treatment.

Genotyping will be shipped to a delegated CRO and analyzed under the responsibility of Bioanalysis-Europe of Astellas Pharma Europe B.V. A separate report will be provided.

The BP-related key secondary endpoints will be analyzed using the post-dialysis BP assessments: MAP and time to first occurrence of increase in blood pressure, similarly with the analyses in Sections 7.4.2.6 and 7.4.2.7 excluding the analysis using All randomized subjects and subgroup analysis.

7.5 Analysis of Safety

Safety analyses will be performed using the Safety Analysis Set (SAF).

Missing dates' imputation rules for AE onset date and stop date are detailed in Section 7.11.2

For each safety parameter, the last non-missing assessment prior to the first dose of study drug will be used as the baseline for all analyses, unless specified otherwise.

For the safety analyses by subgroup, the subgroup analysis by Previous ESA treatment will not be presented in tables, as this analysis is already performed by Type of ESA treatment (Subgroup Darbepoetin and Subgroup Epoetin). In forest plots, results for this subgroup factor Previous ESA treatment will be included.

7.5.1 Adverse Events

All adverse events will be coded using the Medical Dictionary for Regulatory Activities (MedDRA) version 20.0. They will be summarized by System Organ Class (SOC) and Preferred Term (PT).

7.5.1.1 Overview

An overview table will include the following details, by treatment arm and type of ESA treatment:

- Number and percentage of subjects with TEAEs,
- Number and percentage of subjects with causally drug related TEAEs,
- Number and percentage of subjects with serious TEAEs,
- Number and percentage of subjects with serious drug related TEAEs,
- Number and percentage of subjects with TEAEs leading to permanent discontinuation of study drug,
- Number and percentage of subjects with causally drug related TEAEs leading to permanent discontinuation of study drug,
- Number and percentage of subjects with NCI CTC Grade 3 or higher TEAEs,
- Number and percentage of subjects with TEAEs leading to death,
- Number and percentage of subjects with drug related TEAEs leading to death and
- Number of deaths occurring during the Safety Emergent Period and overall.

7.5.1.2 Proportion of subjects with TEAEs by SOC/PT

The number and percentage of subjects with TEAEs, as classified by SOC and PT will be summarized by treatment arm and type of ESA treatment. Summaries will be provided for:

- TEAEs,
- TEAEs (by PT only),
- Drug related TEAEs,
- TEAEs with NCI CTC Grade 3 or higher,
- TEAEs by severity,
- Drug related TEAEs by severity,
- Serious TEAEs,
- Drug related serious TEAEs,
- TEAEs leading to permanent discontinuation of study drug,
- Drug related TEAEs leading to permanent discontinuation of study drug,
- TEAEs leading to death,
- Drug-related TEAEs leading to death,
- TEAEs excluding serious adverse events that equal to or exceed a threshold of 5.0% in any treatment arm (roxadustat or ESA),
- Common TEAEs that equal to or exceed a threshold of 5.0% in any treatment arm (roxadustat or ESA).
- TEAEs by relationship to the study drug,
- AEs occurring during the post study follow up period,
- Serious AEs during the post-study follow up period.

For the summaries by severity or relationship to the study drug, in the subject count, if a subject has multiple TEAEs with the same SOC or PT, but with different severity or relationship, then the subject will be counted only once with the worst severity and highest degree of relationship, however, if any of the severity or relationship values are missing then the subject will be counted only once with missing severity or relationship. In the adverse event count, the adverse events will be presented in each category they were classified to. Drug related TEAEs will be presented in a similar way by severity only.

Maximum severity or relationship will be defined as the worst severity and highest degree of relationship on-treatment (see Section 6.2).

No queries will be done for SMQs.

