### **Post Study Follow-up** (*only for subjects prematurely discontinued from treatment*)

Subjects who have prematurely discontinued study treatment will complete the EOT visits (EOT visit and EOT + 2 weeks visit) and EOS visit. Thereafter, these subjects who have taken at least 1 dose of study treatment, will continue to be followed up at a 6-monthly frequency for vital status, SAEs and cardiovascular and thromboembolic AEs until their projected date of completion of the follow-up period (i.e. projected EOS visit) or until consent withdrawn. Data collection during this poststudy follow-up occur through phone calls or information collected from source data of subjects' regular, non-study, visits to the clinic. No additional study visits will be required from these subjects during the poststudy follow-up. The last poststudy follow-up data collection should occur around the projected EOS visit.

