Investigational period	Period of time where major interests of protocol objectives are observed, and where the test drug or comparative drug (sometimes without randomization) is usually given to a subject, and continues until the last assessment after completing administration of the test drug or comparative drug.

Terms	Definition of terms
Post study follow-up	Period of time from EOS visit to projected week 108 or until consent withdrawn. This period is only applicable to subjects who prematurely discontinued treatment. These subjects will be followed up at a 6-monthly frequency for vital status, SAEs and cardiovascular and thromboembolic AEs.
Pre-investigational period	Period of time before entering the investigational period, from the time of starting a subject enrolling into study until just before the test drug or comparative drug is given to a subject
Randomization	The process of assigning trial subjects to treatment or control groups using an element of chance to determine assignments in order to reduce bias. After randomization subjects receive either roxadustat or ESA (epoetin alfa or darbepoetin alfa) from day 1 until End Of Treatment (EOT).
Roxadustat	International Nonproprietary Name (INN) of ASP1517/FG-4592 investigational product
Re-screening	Process of repeating screening, See also screening and screen failure If subject fails screening they may be re-screened once if deemed appropriate; all screening procedures will be repeated. Renal ultrasound only to be repeated if not within 12 weeks prior to randomization.
Safety Emergent Period	Defined as the evaluation period from the Analysis date of first drug intake up to 28 days after the end of treatment taking into account the different dosing frequencies of the study treatments
Screening	A process of active consideration of potential subjects for enrollment in a trial.
Screening Hb value	Mean of subject's three last Hb values collected during the screening period and prior to the day of randomization.
Screen /Re-screen failure	Potential subject who did not meet one or more criteria required for participation in a trial during screening or re-screening.

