7.5.1.4 Incidence Rates and Cumulative Incidence

Since the percentage of adverse events might be different between treatment arms due to the difference in the discontinuation rates, in addition to the frequency tables above, the incidence rate (per 100 subject years at risk) and the cumulative incidence at 0.5 year, 1 year, 1.5 years & 2 years with the 95% confidence interval, using Greenwood's formula, will be reported by treatment arm and type of ESA treatment.

It will be done for each of the following event types of special interest:

- Serious TEAEs,
- Deaths occurring during the Safety Emergent Period,
- All deaths during study period and post study safety follow up period,
- Related serious TEAEs,
- TEAEs leading to discontinuation of study drug, and
- TEAE NCI CTC Grades 3 or higher.

Hazard ratios of each of the TEAE categories of special interest above will be computed by using Cox Proportional Hazards regression stratified on region, history of CV, previous ESA treatment and adjusted on baseline Hb as continuous covariate. Hazard ratios (roxadustat as relative to ESA) and their 95% CI will be calculated for each TEAE category.

A dot-and-forest plot will be produced showing each of the above TEAE category on the y-axis. The incidence rates by treatment arm, the stratified Cox hazard ratios (roxadustat as relative to ESA) and their 95% CI will be shown on the x-axis.

In addition, cumulative incidence plots for subjects experiencing each of the TEAE categories above will be produced by treatment arm and type of ESA treatment.

Incidence rate (per 100 subject years at risk) for most common PT ($\geq 5\%$ in the total population) by SOC and the cumulative incidences of TEAE by SOC will also be produced for TEAEs in each treatment arm: Cumulative Incidence plots of subjects experiencing each SOC will be produced. A dot-and-forest plot will be produced showing each SOC in the y-axis and the incidence rates, the Cox hazard ratio and its 95% CI in the x-axis. The SOC will be sorted by the hazard ratio.

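### Non-fatal SAEs after early stopping are summarised only as crude percentages, although only early stoppers are followed and for unequal times

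*SAP*

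**What the plan says.** **Who is followed, and for how long.** In the SAP key terms, post-study follow-up is defined as "Period of time from EOS visit to projected week 108 or until consent withdrawn", and "This period is only applicable to subjects who prematurely discontinued treatment". Protocol v3.0 uses the same entry rule but ends the period at the projected EOS visit. Under Protocol 2.2.1.3 these subjects "will continue to be followed up at a 6-monthly frequency for vital status, SAEs and cardiovascular and thromboembolic AEs".

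**How the events are summarised.** The lead-in to SAP 7.5.1.2 reads "The number and percentage of subjects with TEAEs, as classified by SOC and PT will be summarized by treatment arm and type of ESA treatment". Its list ends with "AEs occurring during the post study follow up period" and "Serious AEs during the post-study follow up period". SAP 7.5 makes the SAF the set for safety analyses. Neither post-study table has its own denominator or time at risk.

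**Where exposure adjustment is planned.** SAP 7.5.1.4 adds incidence rates, cumulative incidence and stratified Cox hazard ratios, and gives its reason: "Since the percentage of adverse events might be different between treatment arms due to the difference in the discontinuation rates". One category on its list, all deaths, extends into post-study follow-up; SAP 6.2.1.3 gives the derivation, to Day 760. Serious TEAEs are counted only within the Safety Emergent Period, as are the events per patient-exposure-year in SAP 7.5.1.3. By SAP 7.11.5 that period ends no later than the EOS visit, which is where post-study follow-up begins.

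**Adjudicated events.** Protocol 2.3.3.2 and SAP 7.5.1.6 send adjudicated cardiovascular, cerebrovascular and thromboembolic events to separate analysis plans and reports.

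**The concern.** The post-study follow-up is there to find vital status, SAEs and cardiovascular and thromboembolic AEs after early stopping. For the non-fatal events, this SAP's only summary is a crude percentage. A subject can contribute an event only after stopping early, and has longer to do so the earlier the stop. The percentage mixes three things: the share who stopped, how early they stopped, and the event risk. Only the last is a safety result.

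Unequal stopping is plausible. The trial is open-label and one arm is switched to a new drug while the other continues its own class. One listed reason for stopping treatment, needing a second course of ESA rescue (Protocol 6.1), can apply only to the roxadustat arm. An apparent excess of late SAEs could then arise without any difference in risk, or a real one could be hidden.

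**Working it through.** The documents give no figure to reproduce: no discontinuation rate by arm and no post-study event rate. The check therefore puts the same risk into both arms and asks what the planned table would show.

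**From the documents**
- 375 subjects per arm (SAP 3.3 and Table 2), all taken here as dosed and so in the SAF.
- Follow-up runs from EOS to projected week 108 (SAP). The shortest projected EOS under protocol v3.0 is week 56, that is 52 weeks of treatment plus 4.
- Incidence rate = subjects with event / total time at risk × 100 (SAP 6.2.1.4).

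**Assumed**
- Share stopping early D = 20%, 30% or 40%.
- Constant SAE hazard λ = 0.2, 0.6 or 1.0 per year, equal in both arms.
- Stop week t uniform over the treatment period; EOS four weeks after stopping.

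**Formulas**
- Follow-up in years: F(t) = (P − t − 4)/52.18, where P is the projected EOS week.
- Probability of at least one SAE among entrants, averaged over t: p = 1 − (1 − exp(−λT))/(λT), with T = (P − 4)/52.18.
- Crude percentage of the SAF = D × p.
- Mean time at risk to first event = p/λ.

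**Base case, P = 108, λ = 0.6**
- T = 104/52.18 = 1.993 years and λT = 1.196.
- p = 1 − (1 − 0.302)/1.196 = 0.417.
- D = 20%: 0.20 × 41.7% = 8.3% of the SAF, about 31 of 375.
- D = 30%: 0.30 × 41.7% = 12.5%, about 47 of 375.
- Time at risk: 31.25/0.6 = 52.1 years and 46.88/0.6 = 78.1 years. Rates: 31.25/52.1 and 46.88/78.1, both 60 per 100 subject-years.

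**Range (crude percentage of the SAF, equal risk)**

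| P | λ per year | D = 20% | D = 30% | D = 40% | Rate per 100 subject-years |
|---|---|---|---|---|---|
| 108 | 0.2 | 3.5% | 5.3% | 7.0% | 20 in all |
| 108 | 0.6 | 8.3% | 12.5% | 16.7% | 60 in all |
| 108 | 1.0 | 11.3% | 17.0% | 22.7% | 100 in all |
| 56 | 0.6 | 4.9% | 7.4% | 9.9% | 60 in all |

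**If the denominator is entrants only.** At P = 108 and λ = 0.6 the percentage is 41.7% at every D, so the effect of how many stopped disappears. The effect of when they stopped remains: p is 64.7% if stops fall in weeks 0 to 26, and 24.7% if they fall in weeks 52 to 104.

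**Direction.** With the SAF as denominator, 20% stopping in weeks 0 to 26 gives 0.20 × 64.7%, about 13%. In the other arm, 30% stopping in weeks 52 to 104 gives 0.30 × 24.7% = 7.4%. The arm with fewer discontinuations then looks worse, again at equal risk.

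**The case against.** Several points on the other side stand.

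- **Fatal events are covered.** All deaths, including those in post-study follow-up, get rates, cumulative incidence and hazard ratios. The gap concerns non-fatal events.
- **Adjudicated events have their own plans.** Protocol 2.3.3.2 specifies occurrence and time to occurrence for adjudicated cardiovascular and cerebrovascular events, and SAP 7.5.1.6 sends adjudicated cardiovascular and thromboembolic events to a pooled analysis. A reader might infer that cardiovascular and thromboembolic events after stopping get nothing but crude percentages. The documents do not support that; they leave open whether those plans include post-study events.
- **The denominator is not stated for these tables.** The SAF is the general default in SAP 7.5, but SAP 7.2.1 tabulates completion of post-study follow-up among premature discontinuers only, so a restricted denominator would not be foreign to this plan. It would remove part of the distortion and leave the part due to stopping time.
- **The stakes are bounded.** These are two descriptive tables with no planned test. The main safety comparisons in SAP 7.5.1.4 are time-adjusted, and post-study data are also listed by visit.
- **A rate among entrants is a weak comparison.** Entrants are selected after randomisation, so equal time at risk does not make the arms comparable.

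None of this gives non-fatal post-study SAEs a time-adjusted summary. The reason that SAP 7.5.1.4 gives for rates applies most strongly where entry itself requires discontinuation.

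**Conclusion.** The point holds for non-fatal SAEs, and for cardiovascular and thromboembolic AEs outside adjudication. As planned, their post-study summary is a percentage that depends on the number and timing of early stops and cannot be read as a comparison of risk.

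A reader might infer that the arm with more discontinuations will necessarily show more harm. That does not follow. It needs the SAF as denominator and similar stopping times in the two arms, and the working shows that different stopping times can reverse it.

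The size is illustrative. With equal hazards and the same stopping-time distribution in both arms, the crude ratio equals the ratio of discontinuation rates: 12.5%/8.3% is 1.5, as is 30%/20%. Every discontinuation and event rate used is an assumption. The primary efficacy analyses are not affected. Safety is a secondary objective and SAEs are among the events this follow-up was set up to collect, so the change should be made.

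**What to change.** 1. **SAP 7.5.1.4, with the derivation in 6.2.1.3.** Add time to first SAE from first dose to last contact, including post-study follow-up, by arm. Use the incidence rate, cumulative incidence and stratified Cox model already planned for all deaths over the study and post-study periods. Make this the between-arm comparison, since it starts at first dose and does not condition on stopping. The serious-TEAE analysis stays beside it.
2. **SAP 7.5.1.2.** State that the denominator of the two post-study tables is the subjects who entered follow-up. Add the rate per 100 subject-years by the SAP 6.2.1.4 formula, with time at risk from EOS to first event or last contact. Label it descriptive, because entrants are selected after randomisation.
3. **Cardiovascular and thromboembolic AEs.** Do the same only if a term list is defined and the separate adjudication plans do not already cover post-study events. The SAP gives no such list and plans no standardised MedDRA queries.
4. **End of follow-up.** Reconcile the SAP's projected week 108 with the projected EOS visit in protocol v3.0. The SAP states that it is based on protocol version 2.2.

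The cost is a few more tables and one derivation. SAEs are already collected in this period, and SAP 6.2.1.3 already uses post-study contact dates to censor the deaths analysis. No new data and no change in trial conduct are needed. Item 3 would also need an agreed term list.

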7.5.1.3 Number of Events/100 Patient Exposure Year (PEY)

The number of events and number of events/Patient Exposure Year (PEY) during the Safety Emergent Period with TEAEs, as classified by SOC and PT will be calculated by treatment arm. Summaries will be provided for:

- TEAEs
- TEAE NCI CTC Grades 3 or higher
- Serious TEAEs,

7.5.1.4 Incidence Rates and Cumulative Incidence

Since the percentage of adverse events might be different between treatment arms due to the difference in the discontinuation rates, in addition to the frequency tables above, the incidence rate (per 100 subject years at risk) and the cumulative incidence at 0.5 year, 1 year, 1.5 years & 2 years with the 95% confidence interval, using Greenwood's formula, will be reported by treatment arm and type of ESA treatment.

It will be done for each of the following event types of special interest:

- Serious TEAEs,
- Deaths occurring during the Safety Emergent Period,
- All deaths during study period and post study safety follow up period,
- Related serious TEAEs,
- TEAEs leading to discontinuation of study drug, and
- TEAE NCI CTC Grades 3 or higher.

Hazard ratios of each of the TEAE categories of special interest above will be computed by using Cox Proportional Hazards regression stratified on region, history of CV, previous ESA treatment and adjusted on baseline Hb as continuous covariate. Hazard ratios (roxadustat as relative to ESA) and their 95% CI will be calculated for each TEAE category.

A dot-and-forest plot will be produced showing each of the above TEAE category on the y-axis. The incidence rates by treatment arm, the stratified Cox hazard ratios (roxadustat as relative to ESA) and their 95% CI will be shown on the x-axis.

In addition, cumulative incidence plots for subjects experiencing each of the TEAE categories above will be produced by treatment arm and type of ESA treatment.

Incidence rate (per 100 subject years at risk) for most common PT ($\geq 5\%$ in the total population) by SOC and the cumulative incidences of TEAE by SOC will also be produced for TEAEs in each treatment arm: Cumulative Incidence plots of subjects experiencing each SOC will be produced. A dot-and-forest plot will be produced showing each SOC in the y-axis and the incidence rates, the Cox hazard ratio and its 95% CI in the x-axis. The SOC will be sorted by the hazard ratio.

7.5.1.5 Sensitivity/Subgroup Analyses

= Subgroups of interest:

The number and percentage of subjects reporting TEAEs in each treatment arm will be tabulated by SOC and PT for the subgroups of interest defined in Section [7.8](#)

7.5.1.6 Adverse events up to 7 days after last dose

Additional summaries or analyses with treatment emergent adverse events to be considered restricted to any event starting up to Analysis Date of Last Dose + 7 days considering the last dosing frequency:

- Overview summary table of subjects with AEs
- Number and percentage of subjects with AEs leading to death, as classified by PT

- Incidence rate for serious AEs (i.e., incidence rate, hazard ratios, and cumulative incidence plots as described in Section 7.5.1.4 will be provided)
- Incidence rate for AEs NCI CTC Grades 3 or higher (i.e., incidence rate, hazard ratios, and cumulative incidence plots as described in Section 7.5.1.4 will be provided)
- Number and percentage of subjects with AEs by SOC and PT.

Pre-specified adjudicated cardiovascular and thrombo-embolic events will be analyzed in meta-analyses across multiple phase 3 studies and compared between treatment groups. The statistical method for analysis of the composite safety endpoint (CSE) pooling studies will be detailed in a Meta-Analysis Statistical Analysis Plan. The results will be presented in a separate report.

7.5.2 Clinical Laboratory Evaluation

Descriptive statistics for laboratory values (in SI units) and changes from baseline at each assessment time point and for the maximum and minimum on-treatment (i.e., during Safety Emergent Period) value will be presented by treatment arm and treatment for the quantitative laboratory parameters.

Maximum and minimum on-treatment values will be determined using all the original values and not the derived windows.

Shift tables and number and percentage of subjects with shift to low and shift to high will be reported by treatment arm and type of ESA treatment for the quantitative laboratory parameters.

Box plots of quantitative laboratory values (in SI units) versus visit will be produced by treatment arm (two arms in one page) and type of ESA treatment (darbepoetin alfa and epoetin alfa in another page).

Summary by visit for qualitative laboratory parameters will be provided by treatment arm.

All clinical laboratory data will also be listed.

Potentially clinically significant (PCS) laboratory abnormalities

For each potentially clinically significant (PCS) criterion defined in Section 6.2.3.1 the percentage of subjects with abnormalities by visit and at any moment during the Safety Emergent Period and who did not meet the criteria at baseline will be reported by treatment arm and type of ESA treatment.

Incidence rate (per 100 subject years at risk) and the cumulative incidence at .5 year, 1 year, 1.5 years & 2 years with the 95% confidence interval using Greenwood's formula of PCS abnormalities will also be reported, using only subjects who did not meet the criteria at baseline, by treatment arm and type of ESA treatment. Risk of PCS abnormalities will be compared using the same Cox model as used on Section 7.5.1 Hazard ratio and its 95% will be calculated for the frequency of roxadustat as relative to ESA. A dot-and-forest plot will be produced showing the PCS abnormalities above in the y-axis and the incidence rates, the Cox hazard ratio and their 95% CI in the x-axis.

In addition, cumulative incidence plots for subjects experiencing each PCS abnormality will be produced by treatment arm (two arms in one page) and type of ESA treatment (darbepoetin alfa and epoetin alfa in another page).

